## 5.5. Sample Size

The sample size of 30 is reached by analyzing similar trials in the same field, see the table below where the average sample size is 30 across three comparable trials. Source: Clinicaltrials.gov

Study title	Sample size	Location	Sponsor
Novel Cardiac Signal Processing System for Electrophysiology Procedures	30	Mayo Clinic Texas and Florida	Biosig Technologies Inc.
Clinical Utility and Validation of the Rhythmia Mapping System for the Treatment of Cardiac Arrhythmia	20	Beth Israel Deaconess, Boston	Beth Israel Deaconess, Boston
Feasibility Study of the FARAPULSE Endocardial Multi Ablation System in the Treatment of Persistent Atrial Fibrillation (PersAFOne)	40	Na Homolka, Prague and University Hospital of Split	Farapulse Inc.

## 5.6. Statistical analysis

Endpoint	Statistical method	Hypothesis & benchmark
Freedom from major adverse events, evaluated at hospital discharge.	
 
• Count number of AEs
 
• Percentage: [Procedures with AE] / [Total number of procedures]
 
	
 
• 3.5% of patients develop major AE within 30 days of procedure.
 
• Zero CathVision Cube-related AE are expected.
 

Recording low-voltage electrograms	
 
• Count number of low-voltage electrograms plotted in total
 
• Percentage: [Total number low-voltage electrogram plots] / [Total number of procedures]
 
• Physician user quantitatively score low-voltage electrogram plots on “ease” of interpretation of EGMs” [0-5] on CathVision Cube and on existing EP system 
 
○ 0: Impossible
 
○ 1: Very difficult
 
 
 
	
 
• At least one low-voltage electrogram plot per procedure
 
• CathVision not inferior to existing EP recording system
 

Document no.:	Effective Date:	Version: 1
Author: [name]	Approver:	Reviewer:

Endpoint	Statistical method	Hypothesis & benchmark
	
 
 2: Difficult
 
 3: Possible
 
 4: Easy
 
 5: Very easy
 
 
 
• Average physician score on CathVision ECGenius™ vs average physician score on existing EP system
 
	
Assessing the improved signal quality (baseline noise level peak-to-peak)	
 
• Peak-to-peak amplitude of baseline noise, on unipolar electrogram, at at least 1 site with low-voltage electrograms, and averaged if more than 1.
 
• Peak-to-peak amplitude of baseline noise, on bipolar electrogram, at at least 1 site with low-voltage electrograms, and averaged if more than 1.
 
• Non-inferior peak-to-peak amplitude of baseline noise to existing EP recording system.
 
	
 
• Hypothesis is below 50uV unipolar baseline noise peak-to-peak
 
• Hypothesis is below 20uV bipolar baseline noise peak-to-peak
 
• Hypothesis is non-inferior to existing EP recording system.
 

To visualize the shape and timing of electrograms	
 
• Record activation timing with respect to surface ecg
 
• Classify morphology
 
	Exploratory so no specific hypothesis

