4.7.4 VISIT 2: DAY 0 (INDEX PROCEDURE THROUGH DISCHARGE)

During the index EP procedure, institutional standard of care is to be utilized to treat the subject.

When the subject is connected to the standard EP recording system, during manipulation of catheters or diagnostic tests, intracardiac signals will be recorded using the investigational device in parallel. The total procedure time is not expected to differ by adding the CathVision ECGenius® system to the EP system as the final comparison of data recorded from the Standard EP recording system and the tested device will occur post procedure.

Prior to discharge, the following will be documented:

- Adverse events (AE)
- CathVision ECGenius device malfunctions
- Protocol deviations

Subjects will be considered to have completed and exit the study after this visit.

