4.8 STUDY COMPLETION

4.8.1 COMPLETED SUBJECTS

Subjects will be considered complete when all assessments through the Discharge have been performed in accordance with the protocol. There will be no follow up requirement for this study.

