6.2 ASSESSMENT OF ADVERSE EVENTS

The need to capture AEs is not dependent upon whether or not the clinical event is associated with the use of the study device or procedure. All AEs, regardless of severity, occurring at the index ablation through study completion visit must be recorded. Events occurring prior to the EP procedure must be listed in the cardiac history.

Any Adverse Event(s) that may occur in this study should be reported directly to the Sponsor and IRB, as applicable. Participants experiencing Adverse Events must be treated by the treating physician per standard clinical practice at the institution.

The following information should be obtained for each AE:

1. **Event description.** Every effort must be made to report the underlying condition or unifying diagnosis for the event. To avoid vague, ambiguous or colloquial expressions, the AE should be recorded in standard medical terminology rather than the subject's own words when possible. Signs and symptoms that are considered unrelated to an encountered syndrome or disease should be recorded as individual AEs on the CRF (e.g., if congestive heart failure and severe headache are observed at the same time, each event should be recorded as an individual AE).
2. **Duration:** The date of onset and date of resolution should be reported. Every effort should be made to capture the exact dates.
3. **Outcome:** The final status of the event should be reported as resolved, ongoing, or if it resulted in death. If the event is present at the final study visit, the ongoing box must be marked.
4. **Severity:** The severity of the event must be reported as mild, moderate, or severe using the following definitions:
 - **Mild:** Aware of sign or symptom, but easily tolerated
 - **Moderate:** Discomfort enough to cause interference with usual activity
 - **Severe:** Incapacitating with inability to work or do usual activity
5. **Action taken:** Treatment of the event may be reported as none, medical and/or surgical.
6. **Seriousness:** Determined by using the criteria in Section 6.1.
7. **Relationship to device (study device or ancillary device) and/or procedure.** The relationship to device and study procedure will be assessed using the following criteria.
 - **Not related:** no temporal association or the cause of the event has been identified, or the device or procedure cannot be implicated.

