6.3 REPORTING/RECORDING OF AEs

Throughout the course of the study, all efforts will be made by the investigator to remain alert to possible AEs. The first priority will be the safety of the subject and providing appropriate medical intervention. The period of observation for collection of AEs starts at index procedure until study completion.

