### 5.3. Primary safety endpoints

Freedom from major adverse events, evaluated at hospital discharge.

Document no.:	Effective Date:	Version: 1
Author: [name]	Approver:	Reviewer:

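### The primary safety statistic counts procedures with any AE, while the endpoint is major AEs by discharge and the listed benchmark is a 30-day major-AE rate the study cannot observe

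*SAP*

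**What the plan says.** SAP 5.3 states the primary safety endpoint as "Freedom from major adverse events, evaluated at hospital discharge", and the first row of the SAP 5.6 table repeats it. In that row:

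- The method column asks for a count of AEs and for "Percentage: [Procedures with AE] / [Total number of procedures". Neither item is limited by seriousness, by the word *major* or by relatedness.
- The hypothesis and benchmark column gives two entries: "3.5% of patients develop major AE within 30 days of procedure" and "Zero CathVision Cube-related AE are expected". No source is given for the 3.5%.

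The protocol sets what is captured and for how long:

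- Section 6.2: "All AEs, regardless of severity, occurring at the index ablation through study completion visit must be recorded". Seriousness and relationship to device and procedure are recorded for each event.
- Section 6.3: "The period of observation for collection of AEs starts at index procedure until study completion".
- Section 4.7.4, on the visit that runs from the index procedure to discharge: "Subjects will be considered to have completed and exit the study after this visit".
- Section 4.8.1: "There will be no follow up requirement for this study".

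SAP section 3 contains no definitions. Protocol 6.1 defines AE, SAE, ADE, SADE and UADE, but not major AE. Protocol 7.1 and 7.2 attach no formal hypothesis to the sample size and plan descriptive summaries.

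**The concern.** Safety is part of the primary objective, and this row is the only analysis written for the primary safety endpoint. Followed literally, it reports the proportion of procedures with any recorded AE. Under the protocol's definitions that is an upper bound on the in-hospital major-AE proportion, not an estimate of it.

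The result then sits beside a figure for a different class of event over a longer period. A reader could err in either direction: ordinary minor procedural events could be read as an excess over 3.5%, or a low discharge-only figure could be read as meeting a 30-day rate.

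The second benchmark, zero device-related AEs, can be observed by discharge. But the formula does not separate device-related from procedural events, so that benchmark has no matching statistic either.

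**Working it through.** **Step 1. Set the quantities side by side.**

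| | Event class | Window |
|---|---|---|
| Endpoint (SAP 5.3, 5.6) | major AE | to discharge |
| Statistic (SAP 5.6) | any AE | to discharge (Protocol 4.7.4, 6.3) |
| Benchmark 1 (SAP 5.6) | major AE | 30 days |
| Benchmark 2 (SAP 5.6) | device-related AE | not stated |

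The statistic differs from the endpoint in event class, from benchmark 1 in class and window, and from benchmark 2 in class.

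**Step 2. Reproduce the plan's own figures.** SAP 5.5 takes the sample size as the mean of three trials: (30 + 20 + 40)/3 = 30. This reproduces. The 3.5% has no source or inputs and cannot be re-derived.

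**Step 3. Effect of counting any AE.** With 30 procedures, 1/30 = 3.3% and 2/30 = 6.7%, so two procedures with any AE take the percentage above 3.5%. The documents give no any-AE rate, so p below is an assumption. With X binomial(30, p), P(X ≥ 2) = 1 − (1−p)^30 − 30p(1−p)^29:

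| Assumed any-AE rate p | P(X ≥ 2), n = 30 | P(X ≥ 1), n = 28 |
|---|---|---|
| 5% | 0.446 | 0.762 |
| 10% | 0.816 | 0.948 |
| 20% | 0.989 | 0.998 |

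The last column matters because enrolment is capped at 30, not fixed, and Protocol 4.7.3 counts later screen failures towards it. Since 1/29 = 3.45% and 1/28 = 3.57%, a single procedure with any AE exceeds 3.5% once there are 28 or fewer. These probabilities do not depend on whether any event is major.

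**Step 4. Effect of stopping at discharge.** Suppose the numerator were corrected to major AEs and the true 30-day rate were 3.5%. The share of those events that occurs before discharge is not given, so a range is shown. The in-hospital rate is q = 0.035 × share, and P(0 events) = (1 − q)^30:

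| Assumed share seen by discharge | q | Expected events (30q) | P(0 events) |
|---|---|---|---|
| 100% | 3.50% | 1.05 | 0.34 |
| 75% | 2.63% | 0.79 | 0.45 |
| 50% | 1.75% | 0.53 | 0.59 |
| 25% | 0.88% | 0.26 | 0.77 |

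The smaller the share, the more favourable a discharge-only result looks against 3.5%, with no change in true safety.

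**Step 5. What the study can resolve.** Exact (Clopper-Pearson) two-sided 95% intervals:

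- 0/30: 0 to 11.6%, the upper limit being 1 − 0.025^(1/30)
- 1/30: 0.1 to 17.2%
- 2/30: 0.8 to 22.1%
- 0/28: 0 to 12.3%

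All contain 3.5%. To exclude 3.5% with no events at one-sided 95% would take ln(0.05)/ln(0.965), rounded up to 85 procedures.

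**The case against.** The strongest reply is that *AE* in the formula is shorthand for the row's own endpoint, so one added word would settle it; Protocol 6.2 governs data capture, not the SAP numerator. That reading is possible but not the literal one: the same row writes major AE in one benchmark and plain AE in the other. It would also leave the term undefined and the 30-day mismatch untouched.

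A second reply is that little turns on this. The study is descriptive, no decision rule uses 3.5%, the device records passively and does not direct care, and the informative benchmark is zero device-related AEs. This stands as a limit on consequence: no type I error or power statement is wrong, and crossing 3.5% triggers nothing. But a descriptive estimate must still estimate its endpoint, and the SAP itself lists 3.5% as a benchmark. Protocol 7.2 does allow device-related AEs to be tabulated, but only as a general summary of categorical variables, not as an analysis of this endpoint.

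Third, Protocol 6.5 removes some events from AE status, such as self-limiting pericarditis after ablation, so any-AE may not bound every event someone would call major. Within the protocol's definitions the bound holds, since what is not an AE cannot be a major AE; a definition of major should still address these exclusions.

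Fourth, the any-AE rates are assumed, and Protocol 4.6.1 counts a patient as enrolled only once the criteria are met, which sits uneasily with the screen-failure rule behind the 28-procedure case. Both points are fair: the probabilities illustrate the problem and are not predictions.

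**Conclusion.** The concern holds. As written, SAP 5.6 gives the primary safety endpoint a statistic that does not estimate it, and a numerical benchmark that differs in event class and in a time window the study does not cover.

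The two mismatches with the 3.5% act in opposite directions, and the documents do not allow the net effect to be calculated. The illustrations (45% to 99% chance of exceeding 3.5% at n = 30; 34% to 77% chance of no major AE) rest on assumed any-AE rates of 5% to 20% and assumed pre-discharge shares of 100% to 25%. The interval for 0/30, reaching 11.6%, needs neither assumption and shows that even a clean result neither confirms nor contradicts 3.5%.

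The consequence is misreading of a descriptive safety result. It should be corrected before analysis; it does not affect a stated error rate or subject care.

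**What to change.** 1. Define major AE before the data are analysed, and make the numerator procedures with at least one major AE by discharge. The SAE criteria in Protocol 6.1 are one workable choice. Neither document equates the two terms, so this choice alone would not make the result comparable with the unsourced 3.5%. State how the Protocol 6.5 exclusions are handled.
2. Report any-AE and device-related AE (ADE/SADE) percentages on separate lines, the latter against the existing expectation of zero. Name the relatedness levels that count: Protocol 6.2 classifies possibly related and related events as device effects, but its scale has no level called related.
3. Move the 3.5% out of the benchmark column and label it as 30-day context, not directly comparable. Alternatively, replace it with a sourced through-discharge rate for the same event class.
4. Give each percentage an exact two-sided 95% interval for the actual number of procedures, and state that zero events would not confirm 3.5% or lower (upper limit 11.6% at 0/30, 12.3% at 0/28).

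Cost: SAP wording only if major is defined from seriousness, since seriousness and relatedness are already recorded per event; no extra patients or follow-up are needed. A different definition might need fields not confirmed as collected, and a replacement benchmark needs a source outside these documents. The sponsor gives up any implied claim of meeting 3.5%, and the safety precision will look less favourable.

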## 5.4. Primary performance endpoints

The Primary Performance endpoint of study will be evaluated as technical success of CathVision ECGenius™ System to collect and record intracardiac signals during EP procedures. With focus on:

- To record and plot low voltage electrograms
- To assess the improved signal (better signal to noise ratio) compared with the standard signal
- To visualize the shape and timing of electrograms

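### The low-voltage electrogram count benchmark has no readability criterion and uses a pooled ratio, so it does not show readable recording in each procedure

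*SAP*

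**What the plan says.** The first focus of the primary performance endpoint in SAP 5.4 is "To record and plot low voltage electrograms". The second row of the table in SAP 5.6 makes this operational in two parts.

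- **Count.** The statistic is "Count number of low-voltage electrograms plotted in total", followed by a percentage with total plots over total procedures: "Total number low-voltage electrogram plots] / [Total number of procedures". The benchmark is "At least one low-voltage electrogram plot per procedure". No minimum score is attached, no amplitude defines low voltage, and the count does not name the system it is taken from.
- **Score.** A physician rates ease of interpretation from 0 (*Impossible*) to 5 (*Very easy*), with 3 labelled *Possible*, "on CathVision Cube and on existing EP system". The comparison is "Average physician score on CathVision ECGenius™ vs average physician score on existing EP system", and the benchmark is "CathVision not inferior to existing EP recording system". No margin or test is given, and the row does not say whether both benchmarks must be met.

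Protocol 4.5.1 describes the rating scale differently, from 1 (best) to 5 (worst). Protocol 4.2 has both systems recording in parallel, and Protocol 4.7.4 places the comparison after the procedure.

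**The concern.** The count is the only absolute criterion for this item, and it measures plots produced rather than electrograms that can be read. The study's own reader may call a plot impossible to interpret, and that plot still counts in full.

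The ratio adds a second problem. The benchmark is worded per procedure, but the statistic pools plots over procedures, so extra plots in one procedure make up for none in another.

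The two systems record at the same time, yet the plan specifies no site-by-site agreement between them. A low-voltage site readable on one system and not on the other is visible only through its effect on two averages. A final report could then state 100% success on this benchmark without showing how often the device gave a readable low-voltage electrogram, or whether it did so at the same sites as the standard system.

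**Working it through.** **Inputs from the documents:** 30 procedures (SAP 5.5, where 30 is the mean of three trials: (30 + 20 + 40)/3 = 30); the 0 to 5 scale, ratio and two benchmarks (SAP 5.6). **Assumed:** the scores and plot counts in each scenario, and the cut-off of 3 for readable. The documents give no observed result to reproduce.

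**1. Count benchmark with unreadable plots.** One plot per procedure, all rated 0: 30 plots / 30 procedures = 100%, and every procedure has at least one plot. The benchmark is met. With a cut-off of 3 the result is 0/30.

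**2. Pooled ratio.** 15 procedures with two plots and 15 with none: (15 × 2 + 15 × 0)/30 = 100%. The share of procedures with a plot is 15/30 = 50%. The ratio can also exceed 100%, so it is not a binomial proportion.

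**3. What the score benchmark catches.** The difference is the ECGenius mean minus the existing-system mean.
- 0 against 3: 0 − 3 = −3. This would fail any sensible margin, although none is stated.
- 0 against 0: 0 − 0 = 0. Not inferior on the point estimate, and nothing is readable.
- ECGenius with 10 plots at 0 and 20 at 5: (10 × 0 + 20 × 5)/30 = 3.33, against an existing-system mean of 3.0. ECGenius is ahead on the average. With one plot per procedure, the count is 30/30 while only 20/30 = 67% of procedures have a readable plot. Both benchmarks pass on point estimates.

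**4. Size under a readability criterion.** The exact 95% CI for x of n procedures runs from the 2.5% quantile of Beta(x, n − x + 1) to the 97.5% quantile of Beta(x + 1, n − x). For x = n the lower limit is 0.025^(1/30) = 0.884.

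| Procedures with only plots below 3 (assumed) | Any plot | Readable plot | Exact 95% CI, readable |
|---|---|---|---|
| 0 | 30/30 | 30/30 = 100% | 88% to 100% |
| 3 | 30/30 | 27/30 = 90% | 73% to 98% |
| 6 | 30/30 | 24/30 = 80% | 61% to 92% |
| 15 | 30/30 | 15/30 = 50% | 31% to 69% |

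The any-plot result stays at 30/30 (88% to 100%) in every line.

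**5. How demanding the new criterion is.** If each plot independently scores 3 or higher with probability 0.9 (assumed), all 30 procedures qualify with probability 0.9^30 = 0.042 when there is one plot per procedure, and (1 − 0.1³)^30 = 0.97 when there are three. The number of plots per procedure therefore matters and should be reported.

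**The case against.** The strongest reply is that the row is not judged on the count alone. Unreadable ECGenius plots set against readable standard plots would fail the non-inferiority benchmark under any sensible margin. That stands. A reader might infer that unreadable plots satisfy the whole item, but the documents support this only for the count benchmark. The score comparison remains a partial guard for the reasons in step 3 of the working.

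Other stronger readings also fail:
- A reader might infer that low-voltage electrograms are never counted on the standard recording. The count names no system, so one can say only that a comparator count and a concordance table are not specified.
- A reader might infer that a noisier device would look better because noise can be counted, citing limits such as "Hypothesis is below 50uV unipolar baseline noise peak-to-peak". The same row also hypothesises noise non-inferior to the existing system, so excess noise has its own check. The text leaves room for a noise deflection to be counted; it does not show that this will happen.
- A reader might want each deflection to keep fixed timing to the surface ECG on consecutive beats. Protocol 1.1 names atrial fibrillation among the main ablation arrhythmias. On general electrophysiological reasoning, true atrial electrograms in fibrillation need not keep such timing, so the rule could reject real signals.

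It is also fair to say that the cut-off of 3 is a judgement: scores of 1 and 2 mean difficult, not impossible. That is why a second cut-off is needed. Finally, the study is descriptive and its sample size rests on no formal hypothesis (Protocol 7.1), so reporting count and readability separately is defensible. It still leaves the one absolute benchmark silent on readability.

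**Conclusion.** The concern holds for the count benchmark and its statistic. As written, plots rated 0 meet the benchmark, and the pooled ratio can read 100% when half the procedures have no plot. The score benchmark reduces the risk but does not remove it, because it is relative, has no margin, and compares averages. No per-site concordance between the parallel recordings is specified.

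The size depends on scores not yet known. With 6 of 30 procedures unreadable, reported success falls from 100% to 80%; over the assumed range of 0 to 15 it falls by 0 to 50 percentage points. These figures rest on 30 procedures, at least one plot in each, and a cut-off of 3 on the SAP scale. They show what the rule would let through, not what the device will do.

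**What to change.** 1. Reconcile the scale first. SAP 5.6 runs 0 to 5 with high values good; Protocol 4.5.1 runs 1 to 5 with low values good. Until one direction is fixed, a rule of 3 or higher could select the worse plots.
2. Keep the raw count as a descriptive figure, with the number of plots per procedure.
3. Base the benchmark on the percent of procedures with at least one plot scored 3 or higher on the SAP scale, with an exact 95% CI, in place of the pooled ratio. Report it for each system.
4. Repeat it with a cut-off of 1 or higher as a sensitivity analysis, so that only *Impossible* is excluded.
5. For sites already plotted and scored on both systems, cross-tabulate by procedure: readable on both, ECGenius only, standard only, neither. Do not require a search of both full recordings for every low-voltage site. The table will then not capture sites that were never plotted, and the report should say so.
6. Do not add a fixed-timing rule on consecutive beats.

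The cost is SAP wording and slightly more analysis of scores already planned. The reported success rate may fall.

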4.4.1 INCLUSION CRITERIA

Subjects must meet all of the following inclusion criteria to be included in the study:

1. Patient scheduled for catheter ablation or diagnostic electrophysiology procedure.
2. At least 18 years of age.
3. Able and willing to provide informed consent from a legally authorized representative (LAR).

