6.6 DEVICE MALFUNCTIONS

Device deficiency is defined as an inadequacy of a medical device with respect to its identity, quality, durability, reliability, safety, or performance.

Note, device deficiencies include malfunctions and use errors. All device deficiencies that occur during the trial will be recorded.

Device malfunction: failure of an investigational medical device to perform per its intended purpose when used in accordance with the instructions for use.

User error: act or omission of an act that results in a different medical device response than intended by the manufacturer or expected by the user.

The Device Deficiency CRF is specific for reporting all device deficiencies, or malfunctions that occur during the trial, whether or not they were associated with an adverse event. Device Deficiency CRFs should be submitted to the Sponsor within 24 hours of the occurrence defining the device deficiency.

Anticipated device deficiencies and malfunctions with any standard of care EP system include but are not limited to:

- Catheter deflection deficiency or failure
- Malfunction of a catheter electrode
- Malfunction of a catheter temperature sensor
- Unexpected termination of ablation due to internal system error
- Failure to initiate ablation due to internal system error
- Temporary or sustained loss of catheter navigation/visualization capability/signal

Record any CathVision ECGenius® system deficiencies and malfunctions including but are not limited to:

- ECGenius® system issues (Cube® EPAMP/RecSW)
 - Not able to power on
 - Power indicators not on
 - Not able to connect to the standard of care EP system
 - Not able to retrieve signal from standard of care EP system
 - Not able to power down
 - Database issues
 - Backup data issues
 - Not possible to clear fault without reboot
- ECGenius® Recorder Software
 - Malfunction
 - Loss of power
 - Loss of wave form
 - Recording issues (interruption, stop)
 - Not able to create patient
 - Not able to save patient
 - Live Mode issues (not able to create/resume patient, etc)

- Review Mode issues (not able to retrieve a patient)
- SW crashes
- SW loses connection to EPAMP
- Limitation: Only possible to review the latest recording file, while streaming is active
- Bug: Not possible to use the notch filter, if high-pass and low-pass is set to ‘None’
- Host Computer Malfunctions
 - Not able to boot/start
- User errors
 - Not recording data

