7.2 DESCRIPTIVE ANALYSES

Continuous variables will be summarized using standard quantitative statistics: number of available observations, mean, standard deviation, median, quartiles, and range (minimum and maximum observed values). The number of missing observations, if any, will also be summarized.

Categorical variables will be summarized using classical frequency statistics: number of non-missing observations and percentages by categories. Number and percent of missing data, if any, will also be summarized.

There are no predefined criteria for terminating the study based on statistical outcomes. Missing data will not be replaced or imputed.

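### SAP 5.6: the low-voltage plot percentage is a mean number of plots per procedure and cannot show that every procedure had at least one

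*SAP*

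**What the plan says.** SAP section 5.4 lists "To record and plot low voltage electrograms" first among the three focuses of the primary performance endpoint. The second row of the table in SAP section 5.6 makes this operational with a study-wide count of plots, a ratio and a physician score. The ratio is "Percentage: [Total number low-voltage electrogram plots] / [Total number of procedures]". The benchmark column of that row reads "At least one low-voltage electrogram plot per procedure".

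The first row of the same table, on adverse events, is built differently: "Percentage: [Procedures with AE] / [Total number of procedures]". There the numerator counts procedures.

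The noise row takes its measurement "on unipolar electrogram, at at least 1 site with low-voltage electrograms, and averaged if more than 1", with matching wording for bipolar signals. Protocol section 7.2 gives general rules for summarising continuous and categorical variables and adds "Missing data will not be replaced or imputed".

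**The concern.** The benchmark is a condition on each procedure: it either yielded a plot or it did not. The specified statistic adds up plots over the whole study, so it loses the information on which procedures they came from. It carries the label of a percentage but can exceed 100%, and a value of 100% or more does not show that the benchmark was met.

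Two things are at stake.

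- A report could give 100% or more for a primary performance item although some procedures produced no plot.
- The number of procedures with a plot tells the reader how much evidence lies behind the next measures. The ease-of-interpretation score is given to low-voltage plots, and noise is measured at a low-voltage site. A procedure with neither contributes nothing to those results, and nothing is imputed. The ratio does not supply this number.

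**Working it through.** **Inputs**

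- Number of procedures, n = 30. SAP section 5.5 gives a sample size of 30 as the average of three trials, and (30 + 20 + 40)/3 = 30 reproduces it. Protocol section 4.4 says up to 30 subjects, and the visit schedule has one index procedure each, so 30 is a ceiling.
- Ratio as specified: R = T/n, where T is the total number of plots (SAP 5.6, second row).
- Benchmark: at least one plot in each procedure (same row). Let K be the number of procedures with at least one plot; the benchmark is met when K = n.
- The documents state no numerical result for this row and no distribution of plots per procedure.

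**Can a procedure have more than one plot?** If each gave at most one, R would be a true proportion. Nothing in the documents sets that limit. The wording of the benchmark allows more than one plot, and the noise row provides for averaging over more than one low-voltage site.

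**Bounds that need no distributional assumption**

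For T ≥ 1, K lies between 1 and min(T, n), and at least max(0, n − T) procedures have no plot.

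| Total plots T | Ratio R = T/30 | Procedures with at least one plot, K |
|---|---|---|
| 27 | 90% | at most 27, so at least 30 − 27 = 3 have none |
| 30 | 100% | 1 (1/30 = 3.3%) to 30 (100%) |
| 45 | 150% | 1 (3.3%) to 30 (100%) |

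A ratio of 100% or more is therefore necessary for the benchmark but not sufficient.

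**Constructed patterns, for illustration only**

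| Pattern over 30 procedures | R | K/30 |
|---|---|---|
| 1 plot in each of 30 | 30/30 = 100% | 30/30 = 100% |
| 2 plots in 15, none in 15 | 30/30 = 100% | 15/30 = 50% |
| 3 plots in 10, none in 20 | 30/30 = 100% | 10/30 = 33.3% |
| 2 plots in 29, none in 1 | 58/30 = 193.3% | 29/30 = 96.7% |

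**A less extreme case, under an assumption.** Suppose plots per procedure follow a Poisson distribution with mean m. This is not in the documents. Then the chance of at least one plot is 1 − exp(−m), and the chance that all 30 procedures have one is that value to the power 30.

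- m = 1 (R = 100%): 63.2%, or 19.0 of 30 procedures expected.
- m = 2 (R = 200%): 86.5%; all 30 with probability 1.3%.
- m = 3 (R = 300%): 95.0%; all 30 with probability 21.6%.

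**Precision of the per-procedure proportion.** Exact (Clopper-Pearson) 95% intervals at n = 30:

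- 30/30: 88.4% to 100%. The lower limit is 0.025^(1/30) = 0.884.
- 29/30: 82.8% to 99.9%.
- 27/30: 73.5% to 97.9%.

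**The case against.** The best defence is that nothing turns on the ratio. The benchmark is worded correctly in the same row, and the SAP nowhere says that 100% or more satisfies it. The protocol applies no formal hypothesis to the sample size and has no statistical stopping criteria. Procedure-level data could still be checked against the benchmark. This stands as a limit on severity: the study is not undermined. It does not justify a primary performance statistic that fails to measure its own benchmark.

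A second defence is Protocol 7.2, which calls for the number of available and missing observations and the range. If plots per procedure were summarised, a minimum of 0 would show. If noise is averaged within each procedure, its count of available values would roughly show how many procedures contributed. This is partial cover. Section 7.2 is a general rule that names no variables, the SAP lists only a study total and a ratio, and noise may be missing for other reasons.

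Third, the benchmark might mean an average of one plot. That is the less natural reading, and even then the label of a percentage would be wrong.

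Fourth, the low end of the bounds requires all plots to come from one procedure, which nothing in the documents suggests. That is fair: the bounds show what the ratio cannot exclude, not what is likely.

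Two further points stand. The total number of procedures is not defined for set-ups that failed, and the documents give no voltage threshold for a low-voltage electrogram. A corrected numerator inherits both gaps.

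**Conclusion.** The concern holds. The second-row ratio in SAP 5.6 is a mean labelled as a percentage. It can disprove the adjacent benchmark when it falls below 100% but can never confirm it. At 30 procedures, a reading of 100% or more fits any share from 3.3% to 100% of procedures with a plot. That range rests only on counting and on a procedure being able to yield more than one plot. The constructed patterns and the Poisson figures are illustrations. The point should be fixed before analysis. It is not fatal, because the benchmark itself is stated and can be assessed if plots are recorded by procedure.

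**What to change.** 1. In the second row of SAP 5.6, define the percentage as procedures with at least one low-voltage electrogram plot on ECGenius, divided by the total number of procedures. It then reaches 100% only when every procedure meets the benchmark.
2. State that the denominator includes procedures in which ECGenius did not power on, connect or record, and count these as having no plot. Protocol 6.6 already lists such failures, for example "Not able to connect to the standard of care EP system".
3. Keep the present ratio, relabelled as mean plots per procedure, and report it separately with median and range.
4. List the reason for each procedure without a plot: device failure, or no low-voltage site found. Protocol 4.4.1 admits a "Patient scheduled for catheter ablation or diagnostic electrophysiology procedure", so the absence of a plot need not be a device failure.
5. Add the exact 95% interval as a measure of precision. No test is implied.

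Items 1 to 3 correct the defect; items 4 and 5 help the reader interpret the result.

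**Cost.** One line of the SAP table and a short listing. Device failures are already to be recorded. The SAP calls for a total plot count, so the sponsor should confirm that plots are captured by procedure. The no-low-voltage-site reason may need one tick box on the case report form. The sample size does not change.
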